### Primary estimand (for primary objective)

#### *United States registration*

The *primary* clinical question of interest is:

What is the treatment difference between LY3209590 and insulin glargine in change from baseline at Week 26 in hemoglobin A1c (HbA1c) in study eligible participants regardless of treatment discontinuation for any reason or initiation of rescue therapy?

The *treatment regimen estimand* will be used for the primary objective and is described by the attributes in this table.

Treatment Regimen Estimand Attribute	Description
Treatment condition	Randomized treatment regardless of treatment discontinuation or initiation of rescue therapy
Population	Targeted study population. See Section 3 for detail.
Endpoint	Change from baseline to Week 26 in HbA1c
Remaining intercurrent events	None. The 2 intercurrent events, treatment discontinuation for any reason and initiation of rescue therapy, are addressed by the treatment condition of interest attribute.
Population-level summary	Difference in mean changes between treatment conditions

Abbreviation: HbA1c = hemoglobin A1c.

#### *Rationale for treatment regimen estimand:*

The treatment regimen estimand estimates how participants with type 2 diabetes (T2D) are treated in clinical practice and takes into account both efficacy and safety.

***Registration for countries outside the United States***

The *primary* clinical question of interest is:

What is the treatment difference between LY3209590 and insulin glargine in change from baseline at Week 26 in HbA1c in study eligible participants who adhere to the randomized treatment without an intercurrent event during the study treatment period?

The *efficacy estimand* will be used for the primary objective and is described by the attributes in this table.

Efficacy Estimand Attribute	Description
Treatment condition	Randomized treatment
Population	Targeted study population. See Section 3 for detail.
Endpoint	Change from baseline to Week 26 in HbA1c
Remaining intercurrent events	None. The 2 intercurrent events, treatment discontinuation for any reason and initiation of rescue therapy, are handled by the hypothetical strategy, for example, the potential outcome for those participants if the intercurrent events have not occurred will be estimated
Population-level summary	Difference in mean changes between treatment conditions

Abbreviation: HbA1c = hemoglobin A1c.

*Rationale for efficacy estimand:* The treatment efficacy estimand supports the interpretation of the treatment effect as participants adhere to study treatment.

**Secondary estimands (for multiplicity-adjusted objectives)**

The superiority test in change from baseline to Week 26 in HbA1c will also be based on the primary estimands described above.

The percentage of participants achieving HbA1c <7% at Week 26 without nocturnal hypoglycemia (<54 mg/dL [3.0 mmol/L], or severe) during treatment phase up to Week 26 will be based on a composite estimand. Section 4.4.1.2 contains additional details.

The participant-reported clinically significant nocturnal hypoglycemia (<54 mg/dL[3.0 mmol/L], or severe) is 1 of the safety measures for the study. The event rate will be based on all available data during the specific analysis period. Relative rate between randomized treatment groups will be used for treatment comparison.

**1.2. Study Design**

- Study BDCV is a Phase 3, multicenter, randomized, open-label, comparator-controlled study to evaluate the efficacy and safety of once-weekly basal insulin (LY3209590) compared to insulin glargine in participants with T2D who are on once- or twice-daily basal insulin and at least 2 injections per day of prandial insulin prior to entering the study.

- The study includes a 3-week screening/lead-in period, a 26-week treatment period, and a 5-week safety follow-up period.
- Participants will continue prior stable diabetes therapy with 0 to 3 allowed non-insulin antihyperglycemic medications during the study.
- Participants will discontinue their previous basal insulin doses at randomization and will be assigned to either LY3209590 or insulin glargine, and all participants will be treated with prandial insulin, insulin lispro.
- Assignment to treatment groups will be determined by an interactive web-response system (IWRS). Participants will be randomly assigned to 1 of the 2 treatment groups in 1:1 ratio (LY3209590: insulin glargine) at Week 0 (Visit 3). Stratification will be by country, HbA1c stratum at Week -3 (Visit 1) (<8.0%, ≥8.0%), and routine use of personal continuous glucose monitoring (CGM) or flash glucose monitoring (FGM) at randomization.
- This is a treat-to-target study, both treatment groups will undergo titration to achieve an FBG target within the range of 80-120 mg/dL,. The primary endpoint at Week 26 (Visit 23) is based on participants reaching a stable insulin dose in order to achieve glycemic stability approximately 12 weeks in advance of the 26-week primary endpoint. HbA1c is the primary endpoint and reflects glycemic control from the prior 8 to 12 weeks.
- Rescue therapy will be considered during the treatment period if the participants meet the protocol criteria of severe, persistent hyperglycemia.
- If study intervention is permanently discontinued, the participant will be encouraged to continue participation in the study for continued monitoring. Both efficacy (including HbA1c) and safety data will continue to be collected per the schedule of activities in the protocol.

## 2. Statistical Hypotheses

### Primary Hypothesis

The primary objective of this study is to test the hypothesis that LY3209590 is noninferior to insulin glargine on glycemic control as measured by change from baseline to Week 26 (Visit 23) in HbA1c in participants with T2D currently on basal insulin and at least 2 injections per day of prandial insulin.

Thus, the null hypothesis ( $H_0$ ) to be tested is the difference in the change from baseline to Week 26 (Visit 23) in HbA1c (LY3209590 – insulin glargine) is greater than the noninferiority margin (NIM). The upper bound of the 2-sided 95% confidence interval (CI) will be used for testing the noninferiority.

### Secondary Hypotheses

The key secondary (multiplicity adjusted) objectives are to test the hypotheses that LY3209590 is superior to insulin glargine with respect to

- change from baseline in HbA1c at Week 26  
 $H_0: \text{the difference (LY3209590} - \text{insulin glargine}) > 0.0$
- The percentage of participants achieving HbA1c <7% at Week 26 without nocturnal hypoglycemia (<54 mg/dL [3.0 mmol/L] or severe) during treatment phase up to Week 26  
 $H_0: \text{the odds ratio (LY3209590 vs insulin glargine)} < 1$
- the event rate of nocturnal hypoglycemia (<54 mg/dL [3.0 mmol/L] or severe) during treatment period up to Week 26  
 $H_0: \text{the relative event rates (LY3209590 vs insulin glargine)} \geq 1$

These hypotheses and the primary hypothesis will be tested using a strategy to control the overall type 1 error.

[figure not shown]
### 2.1. Multiplicity Adjustment

A graphical approach (Bretz et al. 2009; 2011) for multiple comparisons will be used to ensure the strong control of the overall type I error rate for testing the primary and key secondary (multiplicity adjusted) objectives.

As illustrated in Figure BDCV 2.1, the primary and key secondary endpoints will be sequentially tested using the primary statistical method described in Section 4.3 to compare LY3209590 and insulin glargine. The overall significance level ( $\alpha$ ) will be set to 0.05. The total  $\alpha$  will be used for the primary objective first, and the noninferiority test for the primary objective will be based on the 2-sided 95% CI. Once the upper limit of the 2-sided 95% CI is below the NIM, the noninferiority is achieved and the  $\alpha$  of 0.05 will be transitioned to test superiority for the key secondary objectives sequentially. If a test in this sequence is not significant, all the subsequent tests will be considered non-significant (Hsu and Berger 1999). This is a predetermined fixed testing order; thus it is a gatekeeper method. The graphical approach is a closed testing procedure; hence, it strongly controls the family-wise error rate (Hsu and Berger 1999; Alosi et al. 2014).

The NIMs of 0.4% (for treatment regimen estimand) and 0.3% (for efficacy estimand) will both be tested to meet different regulatory requirements. No multiplicity adjustments will be made for

conducting separate analyses relative to the efficacy and treatment regimen estimands. Each estimand will have its own family-wise error rate of 0.05.

Abbreviations: NI = noninferiority; HbA1c = hemoglobin A1c; hypo = hypoglycemia; sup = superiority.

**Figure BDCV 2.1. Illustration of graphical multiple testing procedure with initial  $\alpha$  allocation and weights.**

### 3. Analysis Sets

This table defines the populations and data sets for the purpose of analysis.

Analysis Populations/ Data Sets	Description
Entered Population	All participants who sign the informed consent form
Randomized Population	All randomized participants. Participants will be analyzed according to the treatment they were assigned.
Modified Intent-to-Treat (mITT) Population	All randomized participants who took at least 1 dose of study treatment. Participants will be analyzed according to the treatment they were assigned.
Efficacy Analysis Set 1 (EAS1) for treatment regimen estimand on efficacy measures	
The data will include
 
 
• mITT Population, excluding participants discontinuing the study treatment due to inadvertent enrollment, and
 
• all measurements regardless of the use of study treatment or the initiation of rescue therapy.
 

Efficacy Analysis Set 2 (EAS2) for efficacy estimand and for other secondary/tertiary objectives on efficacy measures	
The data will include
 
 
• mITT Population, excluding participants discontinuing the study treatment due to inadvertent enrollment, and
 
• measurements up to the early discontinuation of study treatment or the initiation of rescue therapy.
 
 
The data cutoff for participants who had intercurrent events is defined by the earliest date from below dates for individual participants other than the analysis for study dose:
 
 
• the date of last study dose + 10 days for LY3209590, or +1 day for glargine
 
• the start date of the first treatment of rescue therapy
 
 
The data cutoff for the analysis on study dose is defined by the earliest date from below dates for individual participants:
 
 
• the date of last study dose
 
• the start date of the first treatment of rescue therapy
 

Safety Analysis Set (SS)	
The data will include
 
 
• mITT Population, and
 
• all measurements regardless of the use of study treatment or the initiation of rescue therapy.
 

## 4. Statistical Analyses

### 4.1. General Considerations

Statistical analysis of this study will be the responsibility of Eli Lilly and Company (Lilly) or its designees. Any change to the data analysis methods described in the protocol will require an amendment ONLY if it changes a principal feature of the protocol. Any other changes to the data analysis methods described in the protocol, and the justification for making the change, will be described in this SAP or the clinical study report. Additional exploratory analyses of data will be conducted as deemed appropriate.

Unless otherwise stated, the efficacy analyses will be based on either efficacy analysis set 1 (EAS1, see the definition in Section 3) or efficacy analysis set 2 (EAS2, see the definition in Section 3). For treatment regimen estimand, efficacy analysis set 1 (EAS1, see the definition in Section 3) will be used. For efficacy estimand, EAS2 will be used. The treatment comparison will be based on either 2-sided test or 95% CI.

Unless otherwise noted, the safety analyses will be conducted on Safety Analysis set (SS, see the definition in Section 3). Percentages will be calculated using the safety population as the denominator. For events that are sex-specific, the denominator and computation of the percentage will include only participants from the given sex.

For continuous measures, summary statistics will include sample size, mean, SD, median, minimum, and maximum for both the actual and the change from baseline measurements. For certain variables that are considered to be log-normally distributed, the geometric mean and coefficient of variation (CV) will be provided instead. Either the mixed model repeated measurement (MMRM) model or the analysis of covariance (ANCOVA) model will be used to analyze continuous outcomes. Least-squares (LS) means and standard errors derived from the analysis models will also be displayed. Treatment comparisons will be displayed showing the treatment difference LS means and the 95% CIs for the treatment differences, along with the p-values for the treatment comparisons. For certain safety laboratory measures, log-transformed values will be analyzed in the statistical model instead. The actual change from baseline and percentage change from baseline will be presented using the derivation based on the output from the statistical model and the assumption of log-normality.

For categorical measures, summary statistics will include sample size, frequency, and percentages. Fisher's exact test or logistic regression will be used for treatment comparisons, unless otherwise stated.

For laboratory values, both conventional (CN) and System International (SI) units will be presented. Therefore, both % and mmol/mol will be presented for HbA1c and both mg/dL and mmol/L will be presented for glucose measurements.

In this study, the negative binomial regression will be used to analyze the number of hypoglycemic episodes. Group Mean instead of LS mean will be estimated and delta method will be used to estimate the standard error of the Group Mean (Qu and Luo 2015). Group Mean is defined as the mean response in the treatment group for the studied population. The difference between LS mean and the Group Mean is that LS mean estimates the response by taking the inverse link function on mean covariates, while the Group Mean takes the inverse link function on individual patient covariates first and then averages over all patients. For severe

hypoglycemia, the empirical method based on exposure adjusted rate (calculated by total number of events divided by total exposure) may be used for the treatment comparison if the number of episodes is too small and leads to convergency issues in the negative binomial regression model.

The table below describes the definition of baseline and post-baseline observations for different analyses.

Analysis	Baseline Observations	Post-Baseline Observations
HbA1c (treatment regimen estimand)	The baseline is the last non-missing assessment prior to or on the day of the first dose of study treatment (CRF is used to determine).	Planned measurements at Week 26 (primary endpoint, Visit 23) in EAS1. Use unplanned measurements if no planned measurement.  Multiple imputation approach will be used to impute missing observations at Week 26 (Visit 23).
HbA1c (efficacy estimand)	The baseline is the last non-missing assessment prior to or on the day of the first dose of study treatment.	Weeks 2, 4, 12, 16 and 26 (Visit 5, 7, 15, 17 and 23) in EAS2 for MMRM.  Planned measurements at scheduled visits will be included. Use unplanned measurements if no planned measurement
CGM parameters	The baseline will be derived from the data collected during CGM session prior to the first dose date of study treatment.	The CGM sessions prior to Weeks 4, 12, 26 (Visit 7, 15, 23) in EAS2 for MMRM.  The CGM session prior to Week 26 (Visit 23) in EAS1 for ANCOVA with multiple imputation for missing data.
Basal insulin dose	The baseline period is the screening/lead-in period prior to the initiation of study treatment.  The following variables will be derived: 

• daily dose in U

• weekly dose in U

• dose in U/kg/day

 See detailed derivation of variables in Section 4.4.2.1.	All scheduled visits between Week 0 (Visit 3) and Week 26 (Visit 23) in EAS2 for MMRM.  The following variables will be derived: 

• daily dose in U

• weekly dose in U

• dose in U/kg/day

 See detailed derivation of variables in Section 4.4.2.1.

Analysis	Baseline Observations	Post-Baseline Observations
Prandial (bolus) insulin dose	
The baseline period is the screening/lead-in period prior to the initiation of study treatment.
 
The following variables will be derived:
 
 
• daily dose in U
 
• weekly dose in U
 
• dose in U/kg/day
 
 
See detailed derivation of variables in Section 4.4.2.1.
	
All scheduled visits after Week 0 (Visit 3) and up to Week 26 (Visit 23) in EAS2 for MMRM.
 
The following variables will be derived:
 
 
• daily dose in U
 
• weekly dose in U
 
• dose in U/kg/day
 
 
See detailed derivation of variables in Section 4.4.2.1.

Total insulin dose	
The baseline period is the screening/lead-in period prior to the initiation of study treatment.
 
The following variables will be derived:
 
 
• daily dose in U
 
• weekly dose in U
 
• dose in U/kg/day
 
 
See detailed derivation of variables in Section 4.4.2.1.
	
All scheduled visits after Week 0 (Visit 3) and up to Week 26 (Visit 23) in EAS2 for MMRM.
 
The following variables will be derived:
 
 
• daily dose in U
 
• weekly dose in U
 
• dose in U/kg/day
 
 
See detailed derivation of variables in Section 4.4.2.1.

Basal/total insulin dose ratio	
The baseline period is the screening/lead-in period prior to the initiation of study treatment.
 
See detailed derivation of variables in Section 4.4.2.1.
	
All scheduled visits after Week 0 (Visit 3) and up to Week 26 (Visit 23) in EAS2 for MMRM.
 
See detailed derivation of variables in Section 4.4.2.1.

Fasting glucose by SMBG	
The baseline period is the lead-in period up to the day of first dose of study treatment. Baseline will be derived as the average of all fasting glucose measurements between V2 date and the first dose date.
	
All available data after the day of first dose of study treatment up to Week 26 (Visit 23) in EAS2 for MMRM.
 
Values at each visit will be derived as average of all fasting glucose measurements from the day post prior visit up to the day of the next visit.
 
Data at Week 26 (Visit 23) in EAS1 for ANCOVA with multiple imputation for missing data.

Analysis	Baseline Observations	Post-Baseline Observations
Fasting serum glucose	The baseline is the last non-missing assessment prior to or on the day of the first dose of study treatment.	
All scheduled visits after the day of first dose up to Week 26 (Visit 23) for MMRM
 
Planned measurements at scheduled visits will be included.
 
Data at Week 26 (Visit 23) in EAS1 for ANCOVA with multiple imputation for missing data.

Participant-reported hypoglycemia	The baseline period is the screening/lead-in period prior to the day of first dose of study treatment.	
 
• Treatment period starts on the day of first dose of study treatment and ends 
 
◦ at Week 26 (Visit 23) if completed treatment and Visit 23
 
◦ on the last dose date of study treatment + 10 days for LY3209590, +1 day for glargine if discontinued study treatment early
 
 
 
• Post-treatment period starts from 
 
◦ Week 26 (Visit 23)+1 day if completed treatment and Visit 23
 
◦ last dose date of treatment +11 days for LY3209590, +2 days for glargine if discontinued study treatment early
 
 
 
 
and ends on the last date in the study

TEAEs	The baseline period includes the screening/lead-in period up to the first dose of study treatment (AE Start Relative to Exposure Assessment in CRF is used to determine).	Safety analysis period starts after the first dose and ends at the last visit in the study including safety follow-up period.
Safety laboratory tests, vital signs and body weight	
The baseline will be the last non-missing assessment prior to or on the day of first dose of study treatment
 
Planned measurements at scheduled visits will be included.
	
All scheduled visits after the day of first dose up to Visit 802 for MMRM or ANCOVA
 
Planned measurements at scheduled visits will be included.

Analysis	Baseline Observations	Post-Baseline Observations
laboratory values elevated or low, vital signs and body weight categorical measures	
Starts from the screening visit and ends prior to or on the day of first dose of study treatment.
 
All available measurement at scheduled and unscheduled visits will be included. The baseline for weight will be the last non-missing value during the baseline period
	
Starts after the day of first dose of study treatment and ends at the last visit in the study including both treatment period and follow-up period.
 
All available measurement at scheduled and unscheduled visits in the specified analysis period will be included.

Anti-LY3209590 antibody	The baseline will be the last non-missing assessment prior to or on the day of first dose of study treatment	All scheduled and unscheduled measurement after the day of first dose of study treatment .
Patient-reported outcomes	The baseline will be the data collected at Visit 3	Last collection after Visit 3

Abbreviations: ANCOVA = analysis of covariance; CGM = continuous glucose monitoring; CRF = case report form; EAS1 = efficacy analysis set 1; EAS2 = efficacy analysis set 2; MMRM = mixed model repeated measurement; TEAE = treatment-emergent adverse event.

All analyses will be implemented using SAS Enterprise Guide Version 7.1 or above.

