##### ***Visit 2: Lead-In***

Participants will receive their e-diary, glucometer, and the CGM system.

Participants will receive training on

- diabetes self-monitoring and management
- study glucometer
- CGM
- electronic study diaries, and
- study requirements.

The CGM sensor will be inserted at Visit 2, and participants will be required to wear the sensor when indicated per the SoA.

Starting with Visit 2, participants must measure their FBG levels each day when possible or at a minimum 3 times per week. Starting with Visit 2, participants are strongly encouraged to measure 4-point SMBG profiles at least 3 times per week. Participants will use the study supplied glucometer and e-diary for data collection throughout the study.

Participants will continue their current insulin therapy until randomization. On the day of Visit 3, participants who typically take a morning dose of basal insulin should omit their morning dose of basal insulin as they will receive basal insulin at Visit 3.

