#### **Treatment period**

##### ***Visit 3 (Week 0): Randomization***

This is the general flow for Visit 3:

- Study personnel confirm enrollment criteria

- Participants are randomly assigned to an intervention group
- Study personnel complete baseline procedures and sample collection
- Study personnel will provide dosing training
- Study personnel or the participant will administer the first study dose of LY3209590. Insulin glargine can be taken at the site or after the visit depending upon whether the study visit timing coincides with the participant's usual time to administer basal insulin. Administered insulin doses will be entered into the e-diary
- Study personnel train participants on administering insulin lispro at mealtimes
- Study personnel will download the CGM
- Participant will continue CGM wear per the SoA, and
- Study personnel complete all visit procedures.

All participants will be treated with insulin lispro as prandial insulin throughout the treatment period as described in Section 6.5.3. Participants assigned to insulin glargine will administer glargine daily after Visit 3.

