#### ***Visit 5 through Visit 23 (Week 2 through Week 26)***

Study personnel and participants complete all visit procedures described in the SoA.

The participant's median FBG from the 3 most recent FBGs in the prior week will be used to titrate basal insulin dose adjustments throughout the study based on the study titration algorithm described in Section 6.5.1. Prandial insulin doses should be adjusted as needed.

Participants will collect blinded CGM for

- 4 weeks prior to Visit 7, and the site will download the CGM data at Visit 7
- 4 weeks prior to Visit 15, and the site will download the CGM data at Visit 15, and
- 4 weeks prior to Visit 23, and the site will download the CGM data at Visit 23.

The investigator or study staff will review participant e-diary compliance for

- SMBGs
- hypoglycemia events including related signs and symptoms, and
- dosing information, including date and time of doses.

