##### **4.4.1.1. Definition of Endpoint(s)**

See Section 4.3.1 for change in HbA1c from baseline at Week 26 (Visit 23).

The hypoglycemia events will be based on participant entry into an e-diary, which receives all blood glucose (BG) measurements performed by the participant and transmitted via Bluetooth from the study-provided glucometer. The nocturnal period is defined by midnight to 6 AM. The event rate of nocturnal hypoglycemia will be based on the count of the hypoglycemia episodes in the nocturnal period and the corresponding exposure of study intervention.

Participants achieving HbA1c <7% at Week 26 without nocturnal hypoglycemia (<54 mg/dL [3.0 mmol/L], or severe) during treatment phase up to Week 26 will be a composite measure based on HbA1c measured at Week 26 and nocturnal hypoglycemia reported by participants during the 26-week treatment period.

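### The hypoglycemia treatment period begins on the calendar date of the first dose, so midnight-to-06:00 events before that dose count in two nocturnal key secondary endpoints; the effect is very small and is slight dilution.

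*SAP*

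**What the plan says.** The table of baseline and post-baseline definitions in SAP Section 4.1 sets both boundaries by date for participant-reported hypoglycemia:

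- Baseline: "The baseline period is the screening/lead-in period prior to the day of first dose of study treatment".
- Treatment: "Treatment period starts on the day of first dose of study treatment and ends" at Week 26, or shortly after the last dose if treatment stops early.

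Together these place the whole first-dose date, from 00:00, in the treatment period. SAP Section 4.4.1.1 adds: "The nocturnal period is defined by midnight to 6 AM".

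Protocol Section 4.1 fixes when the first dose happens. In the Visit 3 flow, "Participants are randomly assigned to an intervention group"; later in the same visit, "Study personnel or the participant will administer the first study dose of LY3209590". Glargine may be taken at the site or afterwards, according to the participant's usual dosing time (also Protocol Section 6.5.2.1). Pre-study insulin continues until randomization, and "On the day of Visit 3, participants who typically take a morning dose of basal insulin should omit their morning dose" of basal insulin. The e-diary is dispensed at Visit 2, so an event during the night before Visit 3 can be recorded.

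Other SAP rules treat this day differently:

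- For TEAEs, "Safety analysis period starts after the first dose".
- For fasting SMBG, the first-dose date belongs to baseline.
- For prandial dose, SAP Section 4.4.2.1.2 drops the first day because pre-study and study insulin may be mixed on it.

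**The concern.** An event at, say, 03:00 on the first-dose date normally occurs before any study insulin has been given. The date rule attributes it to study treatment.

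Two of the three key secondary endpoints in the controlled sequence (SAP Sections 2.1 and 4.4.1) use this period: the nocturnal Level 2/3 event rate, and HbA1c <7% without nocturnal hypoglycemia. In the composite, one such event sets the hypoglycemia component to failure for good. Because baseline stops a day earlier, the event is also missing from the baseline nocturnal covariate in both models.

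The definitions can also disagree with each other. A severe event before the dose on that date would be a treatment-period Level 3 event in the hypoglycemia tables but not a TEAE.

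At stake is a slight pull toward no difference and an avoidable misattribution of events.

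**Working it through.** **Timeline for the first-dose date**

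1. 00:00 to 06:00 is the nocturnal window. Under the SAP it is already in the treatment period.
2. Visit 3 takes place (assumed after 06:00). Randomization comes first, then LY3209590 is given on site.
3. Glargine is taken at the visit or later. If its first dose falls on the next calendar date, that date's 00:00-06:00 window is after randomization but still before the dose, unless the dose is taken within those hours.

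**Inputs** (SAP Section 5): 670 randomized 1:1, so 335 per arm; nocturnal rates 0.55 (LY3209590) and 1.1 (glargine) per participant-year, SD 2.6; composite response 42% and 28.7%; 284 completers per arm. The lead-in nocturnal rate L on pre-study insulin is not in the documents. It is assumed here to lie between 0.55 and 5/year, with 1.1/year as reference.

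**The plan's own figures.** The point rests on no stated figure, but the two endpoints carry power claims.

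- Composite: exact two-sided Fisher power at 284 per arm is 0.8999, which reproduces the stated 90%.
- Nocturnal rate: the stated 83% depends on a dispersion and an exposure that the SAP does not give. Wald calculations and simulations under plausible choices run from 0.685 to 0.931, so 83% is not shown to be wrong. The nearest calculation uses glargine-arm dispersion (2.6² − 1.1)/1.1² = 4.68 and 0.5 years. Its variance term is 1/(0.5×0.55) + 1/(0.5×1.1) + 2×4.68 = 14.81, giving power 0.859.

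**Share of nights.** Twenty-six weeks is 182 nights, or 183 dates if both end dates count; 1/182 and 1/183 are both 0.55%. In the Weeks 0-6 analysis, which is outside the controlled sequence, 1/42 = 2.4%.

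**Expected pre-dose nocturnal events per arm** = 335 × L/365.25:

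- L = 0.55: 0.5
- L = 1.1: 1.0
- L = 5: 4.6

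Planned events over 26 weeks are 335 × 1.1 × 182/365.25 = 184 on glargine and 92 on LY3209590.

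**Rate ratio with one pre-dose night included** = (0.55×181 + L)/(1.1×181 + L):

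- L = 0.55: 100.10/199.65 = 0.501
- L = 1.1: 100.65/200.20 = 0.503
- L = 5: 104.55/204.10 = 0.512

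Without that night it is 0.500. In the nearest power model, 0.859 becomes 0.854 at L = 1.1 and about 0.84 at L = 5.

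**Composite.** Only a participant who would otherwise respond can flip. Treating each event as a different participant, expected flips in the trial are 335 × (0.287 + 0.42) × L/365.25:

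- L = 1.1: 0.7
- L = 5: 3.2

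These are probably high, since people with a pre-dose event are likelier to have another on treatment and fail anyway. At L = 1.1 the response rates move from 28.7% and 42.0% to 28.6% and 41.9%, and power by the normal approximation moves from 0.914 to 0.913.

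**The case against.** The case for leaving the text alone has several parts.

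- **Date-level cut-offs are common in the same table.** TEAEs are not a like-for-like contrast, because they use a CRF field recording onset relative to exposure, and no such field is described for e-diary hypoglycemia. This stands as an explanation of the difference. It does not make the pre-dose window on-treatment.
- **The first day is in both numerator and denominator.** Rates use days at risk within the period. True, but the added night is still a night on the old insulin.
- **Starting on the dose date keeps post-dose events later that day.** This matters for the all-day endpoints, and the fix has to respect it. For nocturnal endpoints, the window on that date normally precedes the dose.
- **A pre-dose flag may sit in the ADaM specifications**, which SAP Section 1 places in separate documents. Possible, but the SAP wording does not promise one.
- **Dose times may not be available.** Protocol Section 4.1 has sites review "dosing information, including date and time of doses", yet Section 6.4 requires only amount and date for basal insulin. This stands: a purely clock-based rule could fail for glargine doses first taken off site.

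A reader might also infer more than the documents support:

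- That every nocturnal event on the first-dose date precedes randomization. A first glargine dose on the next date is an exception.
- That 670 × 1.1/365.25 = 2.0 means two misclassified participants. It is two expected events in the trial, with fewer than one expected composite flip.
- That an effect is certain to appear. With 2.0 events expected, the Poisson chance of none is about 13%.
- That an arm is favored or false positives rise. Events before randomization cannot depend on the assigned arm.

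**Conclusion.** The point holds as a small error in the period definition. As written, SAP Section 4.1 counts midnight-to-06:00 events that precede the first dose as on-treatment in two controlled nocturnal endpoints and leaves them out of the baseline covariates. No other passage excludes them.

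At a lead-in rate of 1.1/year, the misassignment costs about 0.5 points of power for the rate and 0.1 points for the composite. Even at the assumed upper end of 5/year, the planning rate ratio is 0.512. The pre-randomization events are non-differential, so the consequence is slight dilution, and it is unlikely to change a conclusion.

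This rests on three assumptions: Visit 3 takes place after 06:00; the first dose usually falls on the Visit 3 date; and the lead-in rate, which is absent from the documents, lies in the range shown.

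**What to change.** Amend the participant-reported hypoglycemia row of SAP Section 4.1:

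1. **Nocturnal endpoints.** Count events and days at risk from the first night after the first-dose date. Assign midnight-to-06:00 events on the first-dose date to baseline. This needs dates only.
2. **All-day endpoints.** Where the first-dose time is recorded, assign same-day events before it to baseline. Otherwise keep the date rule.

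The cost is one extra derivation rule and about one fewer night of nocturnal exposure per participant (0.55%). If a first glargine dose falls on the day after Visit 3, the nocturnal rule puts one post-randomization night in baseline for that participant. The documents do not say how many there will be, so that count should be reported.
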